#### 7.2.8 Visit 8: End-of-Treatment Visit (EoT-Week 36)

End-of-Treatment Visit (V8-EoT) will take place 36 weeks ( $\pm$  6 days) after Randomization Visit (V1). The interval between V7 and V8-EoT must not exceed 48 days.

The following procedures will be completed:

- Log on to IWRS to register patient visit date
- Calculate and record IMP compliance from previous to current visit and review corresponding patient diary
- For T2DM patients, review SMBG measurements (or CGM recording) according to the Investigator (or designee) recommendation
- Record AASLD lifestyle guidance compliance as reported by patient
- Collect AE
- Collect concomitant medications
- Conduct complete physical examination
- Complete pitting edema assessment
- Record vital signs and body measurements
- Perform standard supine single 12-lead ECG
- Following at least a 10-hour fast (food and drink, except water), collect blood and urine specimens for the following:
  - Standard safety laboratory panel (blood and urine)
  - eGFR calculation using CKD-EPI formula
  - FPG
  - HbA1c
  - Measured metabolic parameters
  - Insulin resistance indexes
  - Fibrosis biomarkers
  - Biobanking sampling
  - PK sampling (before IMP intake and between 1h and 4h after IMP intake). The morning meal time after IMP intake should be collected.

- Ensure patient takes the last IMP daily dose on site, in accordance with PK sampling schedule
- Perform MRI-PDFF, before (within 8 days) or on the day of Week 36 (V8-EoT)
- For postmenopausal women only, perform standard DXA testing, before (within 8 days) or on the day of Week 36 (V8-EoT)
- Perform liver biopsy, before (within 8 days) or on the day of Week 36 (V8-EoT),

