AASLD: American Association for the Study of Liver Diseases; AE: adverse event; DXA: dual-energy X-ray absorptiometry; ECG: electrocardiogram; eGFR: estimated glomerular filtration rate; EoS: End-of-Study Visit; EoT: End-of-Treatment Visit; ET: Early Termination Visit; FPG: Fasting Plasma Glucose; HbA1c: glycated hemoglobin; hsCRP: High-sensitivity C-Reactive Protein; ICF: informed consent form; IMP: Investigational medicinal product; IWRs: Interactive Web Response System; lab: laboratory; MRI-PDFF: Magnetic Resonance Imaging - Proton Density Fat Fraction; param.: parameters; phys ex.: physical examination; PK: pharmacokinetics; SMBG: self-monitoring blood glucose; T2DM: Type 2 Diabetes mellitus; V: visit; W: week(s)

- : The interval between two on-site visits must not exceed 48 days.
- : SMBG device dispensed to T2DM patients only. SMBG devices to be brought back to the study site at each visit for measurement review. SMBG device will be kept by the patient after the end of his/her study participation. Continuous Glucose Monitoring (CGM) is accepted and no SMBG device needs to be dispensed in this case.
- : Investigators will explain AASLD guidance regarding diet and exercise at Randomization Visit (V1). Investigators will collect the compliance to this guidance at each subsequent visit.
- : The complete physical examination will include head, ears, eyes, nose, mouth, skin, cardiovascular and lung examinations, lymph nodes, gastrointestinal, musculoskeletal and neurological systems. The limited physical examination will be focused on general appearance, the cardiovascular system as well as towards patient reported symptoms.
- : Vital signs and body measurements include: heart rate and 3 blood pressure measurements in supine or sitting position, and, height (during Screening Period only), body weight, BMI, waist and hip circumferences.
- : Postmenopausal women must have BMD T-score results assessed by standard DXA testing within 6 months prior to Randomization Visit (V1). If there is no available BMD T-score within this period, a DXA testing must be performed during the Screening Period only after receiving confirmation of eligibility on history, clinical examination and labs. DXA testing must also be performed before (within 8 days) or on the day of Week 36 (V8-EoT).

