### 6.2 Dosage and Administration

PXL065 and/or placebo tablets will be taken once daily (QD) in the morning with a glass of water. Patients will take 2 tablets at each administration. For one administration, tablets should be taken together or one after the other. An optimal interval between the daily IMP intakes would be 24 ± 2 hours.

**No IMP should be taken in the morning at home before each visit.** IMP will be taken at study site after all visit assessments are performed as specified in *Table 1* and intake date/time will be recorded in the patient file by delegated staff.

Patients will be provided with the patient diary (paper format) as specified in *Table 1*. All IMP intakes (date and time) will be documented by the patients in the patient diary.

The patient diary is to be returned at each visit together with the IMP kit(s) (used and unused). This also applies to Week 3 (V2), where the patient diary and IMP kits dispensed at Randomization Visit (V1) will be used until Week 6 (V3).

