**Table 2. Treatments to be administered in the 4 treatment groups**

Treatment Group	Number of Tablets (Total = 2 Tablets/Day)
PXL065 7.5 mg QD (7.5 mg/day)	1 tablet of PXL065 7.5 mg + 1 tablet of placebo ( matching PXL065 15 mg tablet )
PXL065 15 mg QD (15 mg/day)	1 tablet of placebo ( matching PXL065 7.5 mg tablet ) + 1 tablet of PXL065 15 mg
PXL065 22.5 mg QD (22.5 mg/day)	1 tablet of PXL065 7.5 mg + 1 tablet of PXL065 15 mg
Placebo	1 tablet of placebo ( matching PXL065 7.5 mg tablet ) + 1 tablet of placebo ( matching PXL065 15 mg tablet )

The double-blind treatment period will last for 36 weeks after Randomization Visit (V1).

The first dose from the new IMP kit dispensed during the visit should be taken on-site during the visit, as detailed in Section 7.2 Double-blind Treatment Period.

The last IMP intake will be at study site on the day of End-of-Treatment Visit (V8-EoT) (morning time; after completion of all pre-dose assessments).

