#### 6.2.2 Follow-up Period

The Follow-up period starts at the end of the 36-week double-blind treatment period. At the End-of-Treatment Visit (V8-EoT), patients will not receive an IMP kit and consequently they will not take IMP during the follow-up period.

The Follow-up period will last for 2 weeks.

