## 6.6 Packaging and Labeling

PXL065 and placebo tablets will be packaged in appropriate blister and will be labeled in English with respect to the regulatory requirements in the United States.

Two tablets, one of each size for the two dosages of PXL065 (15 mg and 7.5 mg, or their respective placebo), should be taken at each intake. The patient must strictly follow these indications.

**IMP kit:** An IMP kit contains 96 tablets (48 days), corresponding to 6 weeks of treatment with 6 additional daily doses to cover time-window between visits; and will be dispensed at each dispensing visit during the double-blind treatment period.

**IMP kit numbering:** The IMP kit number will identify medication packs.

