##### **IMP accountability**

The Investigator (or designee) must maintain an accurate record as follows:

- Site Drug Inventory Log recording IMP receipt, dispensing and return by the CRA to the depot for destruction. The global stock at study site level must be carefully tracked and documented on this log. The Investigator (or designee) should ensure that this stock is consistent with the inventory described in IWRS.
- Subject Dispensing Log recording IMP dispensing and IMP return by patient detailed in terms of number of tablets.

For both logs, dates, quantities, dose, batch numbers, expiry dates and initials of the Investigator (or designee) must be recorded.

The supplies, inventory and accurate IMP documentation must be available for monitoring visit, audit by the designated representatives of POXEL or inspection by regulatory authorities, upon request.

Any unused IMP must not be discarded or used for any other purpose than the present study. IMP that has been dispensed to a patient must not be re-dispensed to the patient neither to a different patient.

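### A V7–V8 interval of exactly 48 days, which the protocol permits, needs 49 daily doses from a 48-dose kit, leaving none for the V8 on-site dose and the post-dose PK sample

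*Protocol*

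**What the plan says.** **Supply.** Protocol Section 6.6: "An IMP kit contains 96 tablets (48 days), corresponding to 6 weeks of treatment with 6 additional daily doses". Section 6.2 sets two tablets per daily dose.

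**Interval.** Section 7.2.8 allows V8 at 36 weeks ± 6 days and adds: "The interval between V7 and V8-EoT must not exceed 48 days". Footnote 1 of Table 1 puts the same limit on all the later visits: "The interval between two on-site visits must not exceed 48 days". SAP Appendix A repeats that footnote.

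**Where each visit's dose comes from.** Section 6.2.1: "The first dose from the new IMP kit dispensed during the visit should be taken on-site during the visit". Section 7.2.7 dispenses one kit at V7. Section 6.2.2 says of V8: "At the End-of-Treatment Visit (V8-EoT), patients will not receive an IMP kit".

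**What V8 requires.** Sections 6.2.1 and 7.2.8 place the final dose on site on the V8 day. Section 7.2.8 asks for one PK sample before that dose and one between 1 and 4 hours after it. Section 6.2 rules out a home dose on the morning of a visit.

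**Leftover tablets.** Section 6.2 has patients bring back every kit, used or not, at each visit. Section 6.7.4 states: "IMP that has been dispensed to a patient must not be re-dispensed to the patient".

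**The concern.** The 48-day cap looks as if it was set to match the 48-dose kit. That match works only when the dose at the closing visit of the interval comes from a new kit. V8 is the one capped visit without a new kit, yet it carries the same cap. At the limit, the V7 kit has to cover one more dosing day than it contains.

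The patient affected is one who has done everything right: a permitted visit date and every dose taken. That patient cannot take the V8 dose that the protocol requires, and so cannot give the 1–4 h sample. Part of a stated secondary objective, the description of pre- and post-dose concentrations after 36 weeks, rests on that sample.

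**Working it through.** **Inputs**

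| Input | Value | Source (Protocol) |
|---|---|---|
| Tablets per kit | 96 | 6.6 |
| Tablets per daily dose | 2 | 6.2 |
| V7 window | Day 211 ± 6 = Days 205–217 | Table 1, 7.2.7 |
| V8 window | Day 253 ± 6 = Days 247–259 | Table 1, 7.2.8 |
| Maximum V7–V8 interval | 48 days, 48 allowed | 7.2.8, Table 1 footnote 1 |
| Kits dispensed at V7 / V8 | 1 / 0 | 7.2.7 / 6.2.2 |

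**1. The plan's own figure.** 96 / 2 = 48 doses, and 6 × 7 + 6 = 48. The kit size is reproduced.

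**2. Counting convention.** Table 1 labels the visit 6 weeks after V1 as Day 43, with V1 as Day 1: 43 − 1 = 42 days. Intervals are therefore differences between dates.

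**3. Doses needed from the V7 kit.** With d = V8 date − V7 date, the kit supplies the V7 dose, d − 1 home doses and the V8 dose, so the need is d + 1.

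| d (days) | Doses needed | Doses in kit | Balance |
|---|---|---|---|
| 42 (nominal) | 43 | 48 | +5 |
| 46 | 47 | 48 | +1 |
| 47 | 48 | 48 | 0 |
| 48 | 49 (98 tablets) | 48 (96 tablets) | −1 |

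**4. Earlier intervals.** The need is only d, because the next visit's dose opens a new kit. At d = 48 that is 48 doses from 48, so nothing is short.

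**5. Is a 48-day interval reachable?** The windows alone allow 247 − 217 = 30 to 259 − 205 = 54 days before the cap. Examples at 48 days are V7 on Day 211 with V8 on Day 259, and V7 on Day 205 with V8 on Day 253.

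**6. How often.** The two windows give 13 × 13 = 169 date pairs. Pairs longer than 48 days number 6 + 5 + 4 + 3 + 2 + 1 = 21, leaving 148 permitted. Exactly 48 days means the V8 offset exceeds the V7 offset by 6, which gives 13 − 6 = 7 pairs.

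- Uniform, independent visit dates: 7 / 148 = 4.73%.
- Normal offsets in whole days, truncated at ± 6: 3.50% with an SD of 3 days, 1.54% with an SD of 2 days.

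The documents give no visit-date distribution, so these spreads are assumptions.

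**7. Patients.** The plan's 24 evaluable patients per arm give 3 × 24 = 72 on active drug. Placebo samples are not assayed. At a 48-day interval there are 47 home doses, and the shortfall arises only if all are taken. With daily adherence q and independent days, that probability is q^47. The documents give no daily adherence rate, so q is also assumed.

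| Daily adherence q | q^47 | Uniform | SD 3 days | SD 2 days |
|---|---|---|---|---|
| 100% (upper bound) | 1 | 3.41 | 2.52 | 1.11 |
| 99% | 0.624 | 2.12 | 1.57 | 0.69 |
| 98% | 0.387 | 1.32 | 0.97 | 0.43 |
| 95% | 0.090 | 0.31 | 0.23 | 0.10 |

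The last three columns are expected numbers of active-arm completers affected.

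**The case against.** The strongest objection is about counting. The protocol never defines whether a 48-day interval includes both visit days. If it does, the interval spans 48 dosing days and the kit is enough. This reading is possible but weaker. The schedule counts weeks as date differences, and under that convention the cap fits the kit exactly at every visit that dispenses a new one.

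Second, the V7 dose could come from what is left of the V6 kit, which would make the V7 kit last. The instruction to open the new kit at the visit is worded as a recommendation. Using the old kit would still depart from it.

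Third, several conditions must coincide: the longest permitted interval, no missed home dose and no interruption of treatment. For PK, the patient must also be on active drug. This stands. The planned interval is 42 days, and the patient counts above rest on assumed spreads and adherence. What the documents themselves establish is that the shortfall occurs on one permitted day.

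Fourth, the consequence is slight. This also stands. MRI-PDFF, the biopsy and the V8 pre-dose sample are unaffected. Membership of the PK population needs only one pre-dose assessment, and the PK objective is descriptive.

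Last, a 47-day cap would turn an otherwise valid day-48 visit into a deviation in all four arms, to protect one sample in three of them. A site instruction to hold back one dose or to book V8 by day 47 would narrow no window. However, holding back a dose means deliberately missing one in the patients concerned, and booking by day 47 is the proposed cap in softer form.

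**Conclusion.** The point holds. On the protocol's own figures, a permitted 48-day V7–V8 interval needs one dose more than the V7 kit contains, and the return and re-dispensing rules close off other sources. It rests on the date-difference count of intervals and on the V7 dose coming from the new kit; the text supports both.

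It is a narrow slip, worth correcting but of low importance. It affects only intervals of exactly 48 days with no missed dose since V7. Across the assumed date spreads and daily adherence of 95% to 100%, that is about 0.1 to 3.4 of 72 active-arm completers. The loss is the V8 on-site dose and the single post-dose sample; no efficacy analysis changes.

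**What to change.** In Protocol Section 7.2.8, set the maximum V7–V8 interval at 47 days and give the reason: the V7 kit must also cover the V8 on-site dose. Make the same exception in footnote 1 of Table 1, which the protocol declares binding where its text is inconsistent, and mirror it in the footnote to SAP Appendix A. Keep 48 days for the earlier intervals.

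At 47 days the need is 48 doses from 48. The cost is one day of scheduling room at V8: 148 − 7 = 141 permitted date pairs remain. No patients, drug or procedures are added. The kit stays at 96 tablets, so the overdose safeguard in Section 6.8 is unchanged. Supplying 98 tablets at V7 would also close the gap, but it would change the kit.

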### 7.3 Follow-up Period, Visit 9: End-of-Study Visit (EoS)

End-of-Study Visit (V9-EoS) will take place 2 weeks ( $\pm$  3 days) after End-of-Treatment Visit (V8-EoT).

The following procedures will be completed:

- Log on to IWRs to register patient visit date
- For T2DM patients, review SMBG measurements (or CGM recording) according to the Investigator (or designee) recommendation
- Record AASLD lifestyle guidance compliance as reported by patient
- Collect AE
- Collect concomitant medications
- Conduct complete physical examination
- Complete pitting edema assessment
- Record vital signs and body measurements
- Perform standard supine single 12-lead ECG
- Following at least a 10-hour fast (food and drink, except water), collect blood and urine specimens for the following:
  - Standard safety laboratory panel (blood and urine)
  - Serum pregnancy test (if applicable)
  - FPG
- Refer patient to his/her previous physician for the pursuit of his/her routine medical care

### 7.4 Early Termination Visit (ET)

The following procedures will be completed during a visit within 8 days after the IMP discontinuation:

- Log on to IWRs to register patient withdrawal date
- Calculate and record IMP compliance from previous to current visit and review corresponding patient diary

- For T2DM patients, review SMBG measurements (or CGM recording) according to the Investigator (or designee) recommendation
- Record AASLD lifestyle guidance compliance as reported by patient
- Collect AE
- Collect concomitant medications
- Conduct complete physical examination
- Complete pitting edema assessment
- Record vital signs and body measurements
- Perform standard supine single 12-lead ECG
- Following at least a 10-hour fast (food and drink, except water), collect blood and urine specimens for the following:
  - Standard safety laboratory panel (blood and urine)
  - Serum pregnancy test (if applicable)
  - FPG
  - HbA1c
  - Measured metabolic parameters
  - Insulin resistance indexes
- Perform MRI-PDFF, before or on the day of Early Termination Visit, if study withdrawal occurs at or after Week 12 (V4) and only when the IMP was discontinued less than 14 days before the ET Visit
- Refer patient to his/her previous physician for the pursuit of his/her routine medical care

## 8 Study Assessments

Every effort should be made to ensure that protocol-required tests and procedures are completed as described.

### 8.1 Blood Volume

The total blood sampling volume for individual patients in this study will be described in the central laboratory manual.

Additional blood samples may be taken for safety assessments at times specified by the Investigator (in case of safety issue for example) with the agreement of POXEL Medical Representative.

### 8.2 Efficacy Assessment

#### 8.2.1 Liver fat mass content assessed by MRI-PDFF – Central imaging core laboratory

The primary evaluation of efficacy will be based on MRI-PDFF. This primary endpoint will be the relative change in the percentage of LFC (assessed by MRI-PDFF) from baseline to Week 36 (V8-EoT).

MRI-PDFF is deemed a non-invasive, quantitative, and accurate measure of LFC to identify the study population and assess the treatment response in subjects with NASH. MRI-PDFF will be performed using a standardized imaging protocol and the results will be analyzed by a central reader. The central reader for this study will train the local imaging centers for this study and will provide imaging manual.

MRI-PDFF reports for Screening Period received by the central core imaging laboratory will be source data to confirm eligibility based on Inclusion criterion #6.

MRI-PDFF will be performed as planned in *Table 1*. MRI-PDFF must be performed only after receiving confirmation of eligibility on history, clinical examination and labs during Screening Period. MRI-PDFF must also be performed before (within 8 days) or on the day on the day of Week 36 (V8-EoT). MRI-PDFF must also be performed at Early termination Visit (ET) only for patients who withdraw from the study at or after Week 12 (V4) and only when the IMP was discontinued less than 14 days before the ET Visit.

MRI-PDFF will be exclusively used for assessment of LFC. The image acquisition technique and programmable sequences used for MRI-PDFF in the study will restrict the obtainable diagnostic information to liver fat quantity and will not support its use for other clinical purposes.

Please refer to central imaging core laboratory manual for further details.

### 8.2.2 Liver biopsy

All patients must have a qualifying liver biopsy within 6 months prior to Randomization Visit (V1). If no available liver biopsy at screening, a liver biopsy must be performed during Screening Period (see Inclusion criterion #7). All patients will have a liver biopsy at Week 36 (V8-EoT).

Histopathological examination of the liver biopsy specimen by a central reader will confirm the diagnosis and provide the staging for the disease. Scores for total NAS, steatosis, ballooning, lobular inflammation, and portal inflammation, as well as fibrosis stage will be evaluated.

Before performing a percutaneous liver biopsy, there must be a clearly defined indication for the biopsy, and the risks to the patient should not outweigh the potential benefits.

The platelet count and INR (or additional blood test) of the patient may be checked at a local clinical laboratory prior to the percutaneous liver biopsy according to local guidelines. If the conditions are not all respected, a safer option would be to perform the liver biopsy by trans-jugular route, when available.

Anticoagulants should be suspended around the time of liver biopsies to reduce hemorrhagic risk, according to local practices.

Sedation is recommended to be given for percutaneous liver biopsy and should be given with caution in liver disease.

The recommended biopsy procedure is as following:

- Needle core biopsy
- 16 or lower gauge needle
- Tissue core  $\geq 2$  cm long ( $\geq 10$  portal tracts) represents optimal biopsy length
- Preferably obtain biopsy from the right lobe. If left lobe biopsy is used for the qualifying biopsy, a left lobe biopsy should be used for future biopsy at Week 36 (V8-EoT).

If the liver biopsy fragment is too small or of bad quality, precluding adequate reading, other available slides or new slides to be prepared from an available block of tissue may be requested of the site.

It is recommended that the patient should remain in the hospital consistent with the standard of care of that institution after the percutaneous biopsy.

Liver biopsy report for Screening Period received by the histopathology central laboratory will be source data to confirm eligibility based on Inclusion criterion #7.

Liver biopsies will be performed as planned in *Table 1*, please refer to Liver biopsy manual for further details.

#### Corporate confidential information

Results from central assessment of liver biopsy should be exclusively used for the purpose of this clinical trial and should not be used for the purpose of patient standard of care.

#### 8.2.3 Other Efficacy Parameters

The following parameters will be also determined at various timepoints to further assess efficacy:

- Liver enzymes: ALT, AST, gamma-glutamyl transferase (GGT), alkaline phosphatase (ALP)
- Measured metabolic parameters: fasting plasma glucose (FPG), HbA1c, serum insulin, C-peptide, adiponectin, total cholesterol, low-density lipoprotein cholesterol (LDL-c), high-density lipoprotein cholesterol (HDL-c), triglycerides and free fatty acids (FFA)
- Insulin resistance indexes: Homeostasis model assessment of insulin resistance (HOMA-IR), Quantitative insulin sensitivity check index (QUICKI), Homeostasis model assessment of  $\beta$ -cell function (HOMA- $\beta$ ) and Adipose tissue insulin resistance (Adipo-IR)

HOMA-IR, QUICKI, and HOMA- $\beta$  will be calculated using the fasting C-peptide and FPG values at visits specified in *Table 1*. Adipo-IR will be calculated using the fasting insulin and FFA values at visits specified in *Table 1*.

The HOMA-IR is calculated as [25]:

$$\text{Serum C-peptide (ng/mL)} \times \text{FPG (mg/dL)} / 405$$

The QUICKI is calculated as [26]:

$$1 / (\log(\text{FPG (mg/dL)}) + \log(\text{C-peptide (ng/mL)}))$$

The HOMA- $\beta$  is calculated as [25]:

$$(\text{Serum C-peptide (ng/mL)} \times 360) / (\text{FPG (mg/dL)} - 63)$$

The Adipo-IR is calculated as [27]:

$$\text{Fasting serum FFA (mmol/L)} \times \text{Fasting serum insulin (\muIU/mL)}$$

- Biomarker of inflammation: hsCRP (assessed as part of Section 8.3.6.1 Standard Safety Laboratory Panel (Blood and Urine))
- Biomarkers of fibrosis: N-terminal type III collagen propeptide (pro-C3), NAFLD Fibrosis score (NFS), Fibrosis 4 (FIB-4) score and Enhanced Liver Fibrosis (ELF) score

The NFS is based on a combination of clinical and laboratory measurements (i.e. age, glycemia, BMI, platelet, albumin and AST/ALT ratio). This score has been validated in a large cohort of patients with biopsy-proven NAFLD ( $> 700$  patients) [28].

NFS is calculated as [28]:

$$1.675 + 0.037 \times \text{age (years)} + 0.094 \times \text{BMI (kg/m}^2\text{)} + 1.13 \times \text{Impaired Fasting Glucose or Diabetes (yes =1; no=0)} + 0.99 \times \text{AST/ALT ratio} - 0.013 \times \text{platelet (10}^9\text{/L)} - 0.66 \times \text{albumin (g/dL)}$$

The FIB-4 score is based on a combination of clinical and laboratory (i.e. age, platelets, AST, ALT). This score has been created and validated in different cohorts of patients [29, 30].

FIB-4 score is calculated as [29]:

$$(\text{Age (years)} \times \text{AST (IU/L)}) / (\text{platelet (10}^9\text{/L)} \times \sqrt{(\text{ALT (IU/L)})})$$

ELF score is an extracellular matrix marker set consisting of tissue inhibitor of metalloproteinases 1 (TIMP-1), amino-terminal propeptide of type III procollagen (PIINP) and hyaluronic acid (HA) showing good correlations with fibrosis stages in chronic liver disease [31].

